2.1 General Methods

If any SAP changes are needed before database lock (DBL), the SAP will be amended. Changes after DBL will be documented in the Clinical Study Report (CSR). If additional supportive or exploratory analyses are requested after SAP approval, this will not require amendment of the SAP, but these additional analyses will be described in the CSR.

Some of the analyses detailed here may be more explicit or in some aspects different from those stated in the protocol. In case of differences, this SAP supersedes the statistical sections in the protocol.

2.1.1 Programming Conventions

Prosoft Clinical will have responsibility for performing analyses. All computations for statistical analyses will be performed using SAS® software, Version 9.4. All SAS programs used in the production of statistical summary outputs will be validated with independent programming prior to finalization. In addition, all program outputs will be independently reviewed. The validation process will be used to confirm that all data manipulations and calculations were accurately done. Once validation is complete, a senior statistical reviewer will perform a final review of the documents to ensure the accuracy and consistency with this plan and consistency within tables. Upon completion of validation and quality review procedures, all documentation will be collected and filed by the project statistician or designee.

The CRF data for all subjects will be provided in Standard Data Tabulation Model (SDTM) datasets. Analysis Data Model (ADaM) datasets will be developed from the SDTM datasets for use in table and figure production.

2.1.2 Reporting Conventions

The formats for the tables, listings, and figures described in this SAP will be provided in a companion document. Changes to the formats of these reports that are decided after the finalization of the SAP will not require an amendment.

All study data from the CRFs as well as derived variables will be provided in subject data listings. Data listings supplied as part of the CSR will be sorted by treatment group, study center number concatenated with subject number, assessment dates, and/or time point. In listings, subjects will be identified by the treatment group in which they were randomized.

The following conventions will be applied to all data presentations and analyses:

- Quantitative variables will generally be summarized by the number of subjects, mean, standard deviation (SD), median, minimum, and maximum. Unless otherwise specified, the minimum and maximum values will be displayed to the same number of decimal places as the raw data, the mean and median will be presented to one extra decimal place compared to the raw data, and the SD will be displayed to two extra decimal places compared to the raw data.

- Categorical variables will be summarized by the number and percentage of subjects within each category. Unless otherwise specified, the percentage will be presented in parentheses to one decimal place. Frequency and percentage values of 0 will be presented as '0' rather than '0 (0)'.
- All summary tables will include the analysis population sample size (i.e. number of subjects) in each treatment group.
- Date variables will be formatted as ISO8601 dates (YYYY-MM-DD) for presentation.
- For analysis of duration of effect and time to onset of treatment response, Kaplan-Meier plots and estimates of the median event times will be used. Responder rates over time will be presented in graphs.

2.1.3 Data Transformations

The Rasch transformation scoring of the [REDACTED] appears in SAP Section 4 below.

2.1.4 Early Termination Visit

For Early Termination (ET) subjects, the Month 6/ET visit will be assigned to the appropriate scheduled timepoint based on the following relative day windowing (where Day 0 is the day of treatment). If a result already exists for the calculated visit or the calculated visit was not a scheduled visit, the next scheduled visit will be assigned.

Study Day Range	Calculated Visit
$1 \leq \text{Study Day} \leq 8$	Day 2
$9 \leq \text{Study Day} \leq 21$	Day 14
$22 \leq \text{Study Day} \leq 42$	Month 1 (Week 4)
$43 \leq \text{Study Day} \leq 70$	Month 2 (Week 8)
$71 \leq \text{Study Day} \leq 98$	Month 3 (Week 12)
$99 \leq \text{Study Day} \leq 126$	Month 4 (Week 16)
$127 \leq \text{Study Day} \leq 154$	Month 5 (Week 20)
$\text{Study Day} \geq 155$	Month 6 (Week 24)

2.2 Analysis Populations

The statistical analyses will be performed based on the following subject populations.

2.2.1 Intent-to-Treat Efficacy Population

The Intent-to-Treat (ITT) population includes all subjects who are randomized and dispensed the investigational product, and will be analyzed according to the randomization scheme. All primary efficacy, secondary efficacy, and exploratory variables will be analyzed based on the ITT population.

2.2.2 Per-Protocol Efficacy Population

The Per-Protocol (PP) population includes all ITT subjects who have no protocol deviations considered to have a substantial impact on the primary efficacy outcome, and will be analyzed

according to the randomization scheme. If the PP population contains less than 90% of the subjects in the ITT, a sensitivity analysis of the primary efficacy endpoint will be performed based on the PP population.

2.2.3 Safety Population

The safety population includes all subjects who were administered the investigational product, and will be analyzed according to as-treated principle. All safety data will be summarized descriptively based on the safety population.

2.3 Study Subjects

2.3.1 Subject Disposition

The number of subjects screened will be shown in total and by study center.

The number of subjects in each study population (i.e. ITT, PP, and Safety) will be summarized by study center and in total (by treatment group and overall).

The disposition of subjects will be presented by study center and in total (by treatment group), including numbers of subjects who were:

- Randomized,
- Completed,
- Withdrawn (including primary reason for withdrawal).

Subject accountability will be summarized by visit with the following:

- Number of subjects expected at each visit (all subjects *minus* number of withdrawn subjects up until that visit)
- Number of subjects completed each visit (all subjects completed that visit)
- Number of subjects missed at each visit (number of expected subjects *minus* the number of subjects completed that visit)
- Number of subjects withdrawn at each visit (all subjects who have withdrawn up until that visit).

2.3.2 Protocol Deviations

Subjects with any protocol deviations will be summarized by study center and in total (by treatment group and overall).

Depending on the seriousness of the deviation, a subject might be excluded from the PP population, which shall be documented prior to database lock. Since the PP population will be used for the primary analysis at Month 1 only, the focus will be on major deviations occurring before and on the Month 1 visit which are considered to have a substantial impact on the primary efficacy outcome. Reasons for exclusion from the PP population will be presented by treatment group and overall.

2.3.3 Demographic Characteristics

Subject demographic data will be summarized for the ITT population by treatment group and overall. Age and body mass index will be analyzed as continuous variables. Gender, race, ethnicity, Fitzpatrick skin type, childbearing potential, and toxin naïve status will be analyzed as categorical variables.

2.5.1 Extent of Exposure

Because subjects will receive a single dose of investigational product, no summary of extent of exposure will be performed. Extent of exposure will be provided in a subject data listing.

2.5.2 Adverse Events

A summary of all AEs (number and percentage of subjects with at least one event and number of events) by treatment group will be provided, which will include:

- Subjects with at least one AE (in total as well as serious AEs).
- Subjects with at least one treatment-related AE (in total as well as serious AEs).
- Subjects with at least one mild, moderate or severe treatment-related AE (in total as well as serious AEs).
- Subjects with at least one unrelated AE (in total as well as serious AEs).
- Subjects with at least one mild, moderate or severe unrelated AE (in total as well as serious AEs).
- Subjects with at least one AE that led to discontinuation (in total as well as serious AEs).
- Number of subjects who did not have an AE.

All other adverse event tables will also be summarized by treatment. Treatment-related AEs, as well as AEs unrelated to study treatment will be summarized by System Organ Class (SOC), PT and maximum intensity.

In addition, for treatment-related AEs, the number of days to onset and the duration of event will be summarized by SOC and PT.

- Time to onset of an AE will be derived as the start date minus the date of the most recent treatment. If the start date is missing, it will be assumed that the AE started on the day of the most recent treatment. If the start month is available but not the day, it will be assumed that the AE started on the first day of the month.
- Duration of an AE will be derived as the stop date minus the start date + 1. If the start date is missing, it will be assumed that the AE started on the day of most recent treatment. If the start month is available but not the day, it will be assumed that the AE started on the first day of the month. If the stop month is available but not the day, it will be assumed that the AE stopped on the last day of the month. Completely missing stop dates will not be imputed and therefore no duration will be calculated in these cases.

AEs that led to discontinuation from the study will also be summarized.

Serious AEs and treatment-related AEs with late onset (i.e. AEs with onset > 21 days after treatment) will be listed.

For subject counts, a subject will only be counted once per SOC and once per PT in cases where multiple events are reported for a subject within SOC or PT. For event counts, subjects with multiple events in a category will be counted for each event.

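### SAP 2.5.2 sets a completely missing AE start date to the treatment day and then treats it as a measured onset: time to onset is always 0, duration can be overstated, and a non-serious related event of unknown onset cannot reach the late-onset listing

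*SAP*

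**What the plan says.** SAP 2.5.2 plans summaries of days to onset and of duration for treatment-related AEs, by SOC and PT. Protocol 9.1.3.1 asks for the same two summaries.

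- Onset: "Time to onset of an AE will be derived as the start date minus the date of the most recent treatment".
- Duration: "Duration of an AE will be derived as the stop date minus the start date + 1".
- Missing start, for onset: "If the start date is missing, it will be assumed that the AE started on the day of the most recent treatment".
- Missing start, for duration: "If the start date is missing, it will be assumed that the AE started on the day of most recent treatment".
- Month known, day unknown: "If the start month is available but not the day, it will be assumed that the AE started on the first day of the month". Because this case has its own rule, the missing-start rule is left with dates for which no month is known.
- Missing stop: "Completely missing stop dates will not be imputed and therefore no duration will be calculated in these cases".
- Listing: "Serious AEs and treatment-related AEs with late onset (i.e. AEs with onset > 21 days after treatment) will be listed".

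The visible text has no exception, flag, count of imputed values or check against the stop date for an imputed start. SAP 1.6 classes an AE as treatment-emergent if its onset is at or after dosing, and gives no rule there for a missing onset. Both documents say safety data are analysed on observed cases (Protocol 9.1.2.4; opening of the SAP's Safety Analysis section).

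**The concern.** Dating an event of unknown start to the dosing day is a cautious choice when the question is whether the event counts as treatment-emergent. It is not a cautious choice when the same date is read as a measurement. It gives the smallest possible post-treatment onset and, where a duration can be computed, the largest possible post-treatment duration. Both values then enter summary statistics with nothing to mark them as assumed.

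The late-onset listing is the output meant to bring delayed related events to the reader's attention. Under this rule an event of unknown timing is counted as having occurred at once, even if its own stop date leaves a late onset entirely possible. Time to onset and duration are named AE endpoints in SAP 1.6, and PT-level cells may hold only a handful of events, so one assumed zero can move a median.

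**Working it through.** **Inputs.** All rules come from SAP 2.5.2. Protocol 6.1.7.6 gives one study treatment, at baseline, and SAP 2.1.4 numbers that day as Day 0. The start and stop days below are assumed for illustration. The documents give no number of AEs with missing start dates and no figure to reproduce on this point.

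**Formulas.** Let *s* be the true start day and *e* the stop day, both counted from dosing.

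- True onset = *s*. Onset under the rule = 0 − 0 = 0.
- True duration = *e* − *s* + 1. Duration under the rule = *e* − 0 + 1 = *e* + 1.
- Overstatement of duration = (*e* + 1) − (*e* − *s* + 1) = *s*, the true onset day.
- Listing criterion under the rule: 0 > 21, which is false for every stop date.

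**Single events.**

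| Start, stop (day) | True onset | Onset under rule | True duration | Duration under rule | Meets >21 days: true / rule |
|---|---|---|---|---|---|
| 0, 3 | 0 | 0 | 4 | 4 | no / no |
| 10, 14 | 10 | 0 | 5 | 15 | no / no |
| 22, 26 | 22 | 0 | 5 | 27 | yes / no |
| 30, 40 | 30 | 0 | 11 | 41 | yes / no |
| 100, 104 | 100 | 0 | 5 | 105 | yes / no |
| 150, 168 | 150 | 0 | 19 | 169 | yes / no |
| 30, no stop date | 30 | 0 | none | none | yes / no |

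The first row shows that nothing changes when the event really began on the dosing day. The last row shows that duration is untouched when the stop date is completely missing.

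**Stop date before dosing.** With a stop 3 days before treatment, the rule gives −3 − 0 + 1 = −2 days, an impossible duration.

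**Worst case for a small PT cell.** Take four related events with true onsets of 2, 5, 10 and 45 days.

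- True values: median (5 + 10)/2 = 7.5; mean 62/4 = 15.5.
- Start of the fourth missing: values 0, 2, 5, 10; median (2 + 5)/2 = 3.5; mean 17/4 = 4.25.
- If the fourth event stopped on Day 47, its duration goes from 47 − 45 + 1 = 3 to 47 − 0 + 1 = 48 days.
- Events meeting the late-onset criterion go from one to none.

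This example makes the most extreme value the missing one. If the Day 2 event were the one without a start date, its onset would shift by 2 days and so would its duration.

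**Frequency.** If 0 to 2% of AEs lacked a start month (an assumption), that would be 0 to 2 events in every 100.

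**The case against.** The strongest reply is that the rule will hardly ever be used. Protocol 7.2.2.2.1 makes date of onset a requested item on the AE form and has subjects asked at each visit about changes since the last one. Protocol 10.3 has data clarifications resolved before lock. Someone who can date the end of a short event can usually name the month in which it began. This stands, and it limits the size of the point.

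A second reply is that the rule is pre-specified and reproducible, that no inferential safety analysis is planned, and that incidence, severity, seriousness and relatedness do not depend on the imputed duration. Possible remote-spread events are found by preferred term and reviewed medically under SAP 2.5.3, without using the 21-day listing. This also stands. It does not make a Day 0 onset correct for an event whose start is unknown.

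A reader might infer more than the documents support:

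- **That such events disappear from the report.** They do not. SAP 2.1.2 puts all CRF data and derived variables in subject listings, where the blank start date can be seen.
- **That no such event, serious or not, can be listed under this sentence.** The sentence can be read as listing all serious AEs plus related AEs with late onset. On that reading a serious event is still listed as serious, though not as late.
- **That every such event has an inflated duration.** This needs a stop date or stop month, and a true onset after dosing.
- **That treating start and stop dates differently is a contradiction.** A missing stop date can mean the event is ongoing, so there is a reason not to impute it.

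**Conclusion.** The point holds as a small, inexpensive improvement. For an AE whose start month is unknown, SAP 2.5.2 fixes onset at 0 and, where duration can be computed and the event followed dosing, overstates duration by the true onset day. A non-serious related event dated this way cannot meet the criterion behind "treatment-related AEs with late onset (i.e. AEs with onset > 21 days after treatment) will be listed". Putting an assumed date into onset and duration statistics also fits poorly with the observed-cases principle stated for safety data.

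The effect is confined to descriptive timing summaries and one listing, and it probably concerns very few events, possibly none. The conclusion rests on reading the missing-start rule as applying when no month is known, and on there being no exception elsewhere in the visible SAP. The four-event illustration is a worst case, not an expected effect.

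**What to change.** In SAP 2.5.2, replace the two missing-start sentences with the following rules, taking a completely missing start date to mean that no month is known.

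1. Use the treatment-day date only to class the AE as treatment-emergent, and do not use it when the recorded stop date is before dosing.
2. Summarise time to onset and duration on events with a start date that is at least partly known. Show, by treatment group, how many events were left out because the start date was completely missing.
3. List treatment-related AEs with a completely missing start date beside the late-onset listing, under a separate onset-unknown flag, unless the recorded stop date shows that onset was on or before Day 21.

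The flag in item 3 is needed because leaving the date blank would also keep the event out of the listing. The stop date is used for the check because it is already part of the SAP's duration rule, whereas the visible text does not show that the visit of first report is captured on the AE form.

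The cost is a short SAP edit and a small programming change. A few descriptive cells may lose an event, and the listing may gain a few events of unknown timing.

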## 1.4 Risk/Benefit Assessment

In the Dysport clinical development program for the treatment of glabellar lines the majority of adverse events (AEs) were mild or moderate in severity, transient, and not considered related to study treatment. In clinical trials, the most frequently reported TEAEs considered related to Dysport treatment were headache, injection site reactions and eye disorders, and the adverse reaction (ADR) profile from postmarketing experience is similar to the safety profile observed in the clinical study program. The identified risks associated with treatment of glabellar lines with botulinum toxin type A haemagglutinin complex (BoNT-A-HAC) include eye disorders and spread of effect of the toxin beyond the areas of injection.

In clinical trials in glabellar lines, ocular TEAEs were reported at the following frequencies: common (i.e.  $\geq 1\%$  and  $< 10\%$ ), asthenopia, eyelid ptosis, eyelid edema, increased lacrimation, dry eyes and muscle twitching around the eyes; uncommon (i.e.  $\geq 0.1\%$  and  $< 1\%$ ), blurred vision, diplopia, visual disturbances and eye movement disorders. The most commonly reported eye

 GALDERMA	Title 43USD1805 Clinical Study Protocol Dysport New Dilution GL	Doc id [REDACTED]
--	---	----------------------

disorders from postmarketing data were eyelid ptosis, vision blurred, eyelid edema, eye swelling and diplopia.

Adverse effects resulting from the distribution of the effects of the toxin to sites remote from the site of administration have been reported. The risk of occurrence of such undesirable effects may be reduced by using the lowest effective dose possible and by not exceeding the maximum recommended dose. Very rare cases of death, occasionally in the context of dysphagia, pneumopathy (including but not limited to dyspnea, respiratory failure, respiratory arrest) and/or in patients with significant asthenia have been reported following treatment with botulinum toxin A or B. Patients with disorders resulting in defective neuromuscular transmission, difficulty in swallowing or breathing are more at risk of experiencing these effects.

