1.6 Safety Endpoints

Safety endpoints include:

1) Treatment Emergent Adverse Events

Adverse events (AEs) are to be monitored throughout the course of the study. The study period for the purpose of AE collection is defined as the period from the signing of a study specific informed consent to study exit for a subject. AEs recorded on the electronic case report forms (CRFs) will be coded using the Medical Dictionary for Regulatory Activities (MedDRA) Version 22.0. AEs will be classified as treatment emergent adverse events (TEAEs) if the AE had an onset time greater than or equal to the time of the dose of study treatment.

AE endpoints include:

- Incidence,
- Causality (related/not related to investigational product),
- Intensity (mild/moderate/severe),
- Time to onset,
- Duration,
- Leading to study withdrawal,

- Seriousness.

2) Focused Physical Examination

At screening, baseline, Days 2 and 14, and Months 1 and 6, the Investigator or designee will perform a physical examination of the subject that includes the face and neck. The Investigator may choose to investigate any other sign that he/she observes during the physical examination and should assess all abnormal findings for clinical significance.

2 Statistical Methods

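### SAP 2.5.2 moves a partial AE stop date to month-end with no bound at last contact or death, so some imputed stop dates are impossible

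*SAP*

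**What the plan says.** SAP 2.5.2 defines duration: "Duration of an AE will be derived as the stop date minus the start date + 1". For a partial stop date it says: "If the stop month is available but not the day, it will be assumed that the AE stopped on the last day of the month". A partial start date goes the other way: "If the start month is available but not the day, it will be assumed that the AE started on the first day of the month". A stop date with no month is left alone: "Completely missing stop dates will not be imputed and therefore no duration will be calculated in these cases".

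The result is tabulated: "for treatment-related AEs, the number of days to onset and the duration of event will be summarized by SOC and PT". SAP 1.6 lists duration among the AE endpoints. The general convention in SAP 2.1.2 is: "Quantitative variables will generally be summarized by the number of subjects, mean, standard deviation (SD), median, minimum, and maximum".

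Two passages bear on when observation ends. SAP 1.6 closes AE collection when the subject leaves the study. Protocol 7.2.2.2.1 follows AEs judged related to treatment or procedure to resolution or stability, and follows other unresolved AEs only up to the last visit.

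No readable passage limits the imputed stop date at last contact, study exit or death. Parts of the SAP are redacted, so a general date convention there cannot be ruled out. The duration rule in 2.5.2 is legible, however, and contains no limit.

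**The concern.** A stop month can be entered only once someone has learned that the event is over. Its true stop date therefore cannot be later than the last contact at which the subject's status was recorded, or later than death. Month-end ignores that bound. If the subject was last in contact early in the same month, the rule creates a stop date that the trial's own records rule out, and the duration formula then treats it like an observed date.

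At stake is the accuracy of a listed safety endpoint, duration of treatment-related AEs by SOC and PT. Where a preferred term has few events, one such record can set the reported maximum and move the mean. The median is also planned and is less sensitive. The error can only lengthen the duration.

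**Working it through.** The plan states no figure to reproduce, so the check applies its rule directly.

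**Inputs from the documents**
- Duration = stop − start + 1 (SAP 2.5.2).
- Partial stop date = last day of the known month (SAP 2.5.2).
- Month 6 corresponds to Week 24 (SAP 2.1.4), so a nominal final visit is at 24 × 7 = Day 168.

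**Assumptions, because the documents are silent**
- The date of last contact (or death) is uniform over a 365-day year.
- Last contact is on Day 168 in step 3.
- The share of AEs with a partial stop date is not given, so results are per affected event.

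**Step 1. How far past the last possible date.** Take a month of L days with last contact on day c of that month, which is also the AE's stop month. The imputed date is L − c days too late to be possible.
- Maximum, at c = 1: L − 1 = 27, 29 or 30 days for L = 28, 30 or 31.
- Mean within a month: (L − 1)/2 = 13.5, 14.5 or 15.0 days.
- Mean over the year: (7 × 31 × 30/2 + 4 × 30 × 29/2 + 28 × 27/2)/365 = (3255 + 1740 + 378)/365 = 5373/365 = 14.7 days.
- Share of days on which month-end is later than contact: (365 − 12)/365 = 96.7%.

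**Step 2. One record.** A related AE starts on 3 May. The subject's last recorded contact is 5 May, with the AE recorded as over and only May known as the stop month.
- Under the SAP: 31 − 3 + 1 = 29 days.
- Longest duration compatible with the record: 5 − 3 + 1 = 3 days.
- The imputed stop date is 31 − 5 = 26 days after last contact.

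**Step 3. What a cap changes.** Take a true 2-day AE with a known start and an unknown stop day, averaged over every treatment date in a year, with last contact on Day 168.

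| Onset day | Cap binds | Mean duration, no cap | Mean duration, capped |
|---|---|---|---|
| 0, 7, 14, 30 or 90 | 0% | 16.7 | 16.7 |
| 150 | 41% | 16.8 | 14.0 |
| 160 | 74% | 16.7 | 8.1 |

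The 16.7 is the true 2 days plus an average month-end overstatement of 14.7. The cap acts only when the stop month is also the month of last contact. In a subject who leaves early that month comes sooner, so the cap could then bind for an early event too. That case was not calculated.

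**The case against.** The strongest reply is that month-end is a deliberate longest-duration convention. It is prespecified, applies equally to both arms, and feeds a descriptive table with no planned inference. SAP 2.1.2 puts CRF data and derived variables in listings, so affected records should be traceable there. Data-management edit checks should keep partial dates few. Related AEs are followed past exit, so a stop date after the final visit is not in itself wrong.

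All of this stands, and it sets both the low materiality and the choice of bound: last recorded contact including post-exit follow-up, not the Month 6 visit. It does not defend a stop date later than any contact at which the event could have been recorded as over. A longest-duration convention should return the longest duration the record allows.

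A reader might infer more than the documents support:
- **That the missing cap explains month-long durations for short AEs generally.** Step 3 shows it does not. With follow-up to Day 168 the cap never binds for the onsets tested through Day 90, and the excess there comes from the month-end convention itself.
- **That a same-month event with both days unknown, always counted as 28 to 31 days, shows the same fault.** That result also needs the separate first-of-month start rule.
- **That the percentage bias in the mean can be stated.** It would need the true mean duration and the share of partial dates, and neither is given.
- **That the protocol calls related AEs transient.** Protocol 1.4 says "the majority of adverse events (AEs) were mild or moderate in severity, transient, and not considered related to study treatment", which describes AEs in the development programme generally.
- **That the summary should use complete dates only.** This would drop events from a safety table, and a cap would then change no summary value.

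**Conclusion.** The point holds as a narrow one. Where the stop month is the month of last recorded contact or death, the readable SAP rule can impute a stop date up to 30 days after the last possible one. With that date uniform over the year, the excess averages 14.7 days and occurs on 96.7% of days. The value enters the duration summary for treatment-related AEs.

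Materiality is low. How many events are affected depends on the share of partial dates, which is not stated. For events that end before the month of last contact the cap does nothing. Month-end remains a conservative convention there, about 14.7 days too long on average if the stop day is uniform over the month. No inferential result or comparison between arms depends on this. The conclusion also assumes that no redacted passage supplies a bound.

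**What to change.** Amend the stop-date rule in SAP 2.5.2 along these lines: when the stop month is known and the day is not, the stop date is the earliest of (a) the last day of that month, (b) the date of the subject's last recorded contact, including any post-exit follow-up of a related AE under protocol 7.2.2.2.1, and (c) the date of death; it is never earlier than the start date. The floor guards against inconsistent records.

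Keep the capped durations in the SOC and PT summary. Beside it, show the number of events whose duration used an imputed day, so that a reader can see how much of each row rests on imputation.

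The cost is one amended sentence, a small programming change and one extra count in the table. No event leaves the summary. SAP 2.1 provides for amendment before database lock.
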